7.2.1. Dosing Schedule

Refer to Section [7.2.2](#) for Part A (dose escalation) dose regimens for each combination, by cohort. Refer to Section [7.2.3](#) for Part B (disease-specific expansion) dose regimens for LY3022855-plus-durvalumab, by cohort.

For each combination regimen, LY3022855 will be administered first, followed by a 30-minute observation period. After the observation period, durvalumab or tremelimumab will be administered. In this study, a cycle is defined as 4 weeks (28 days); Day 1 of a cycle is based on the administration of LY3022855 (rather than durvalumab or tremelimumab). A delay of study treatment due to holiday, weekend, bad weather, or other unforeseen circumstances will be permitted for a maximum of 3 days and not counted as a protocol deviation.

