7.2.1.2. Durvalumab

Patients are to receive durvalumab I.V. on Days 1 and 15 of every cycle. Durvalumab may be administered up to 3 days AFTER the scheduled dosing date. If, at any time, a dose is administered beyond the 3-day window, that dose is considered a dose delay. A maximum delay of 28 days between administered doses is allowed (for dose delay in case of immune-related AE

please refer to Section 7.2.4.1). Note that a maximum of 12 months/26 doses of durvalumab treatment is permitted.

Refer to [Attachment 9](#) for the durvalumab dose volume calculation.

Durvalumab will be administered at room temperature (approximately 25°C) by controlled infusion via an infusion pump into a peripheral or central vein. Following preparation of durvalumab, the entire contents of the I.V. bag should be administered as an I.V. infusion over approximately 60 minutes (± 5 minutes), using a 0.2- or 0.22- μ m in-line filter. Less than 55 minutes is considered a deviation.

The I.V. line will be flushed with a volume of I.V. solution (0.9% [w/v] saline) equal to the priming volume of the infusion set used after the contents of the I.V. bag are fully administered, or complete the infusion according to institutional policy to ensure the full dose is administered and document if the line was not flushed.

A 1-hour observation period is required after the first infusion of durvalumab. If no clinically significant infusion reactions are observed during or after the first cycle, subsequent infusion observation periods can be at the investigator's discretion (suggested 30 minutes after each durvalumab infusion).

Patients will be monitored during and after the infusion with assessment of vital signs at the times specified in this study protocol.

In the event of a Grade ≤ 2 IRR, the infusion rate of study drug may be decreased by 50% or interrupted until resolution of the event and re-initiated at 50% of the initial rate until completion of the infusion. For patients with a Grade ≤ 2 IRR, subsequent infusions may be administered at 50% of the initial rate. Acetaminophen and/or an antihistamine (for example, diphenhydramine) or equivalent medications per institutional standard may be administered at the discretion of the investigator. If the IRR is Grade ≥ 3 in severity, study drug will be permanently discontinued.

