Coagulation (local)							Refer to Attachment 2. As clinically indicated.
Thyroid function (central)	X						Refer to Attachment 2 . Free T3 and free T4 will be measured only if TSH is abnormal or if there is clinical suspicion of an AE related to the endocrine system.
Pancreas function (central)							Refer to Attachment 2.
Tumor markers (local)							
Pharmacogenetic sample	X						Refer to the laboratory manual. Collect once. Sample can be collected at any time, if not collected on C1D1.

LY3022855 plus Durvalumab Assessment (central or local laboratory indicated, if applicable)	Cycle 1 (Visit 1)						Comments Except for the Cycle 1, Day 1 visit, allowable windows are ± 3 days, unless otherwise indicated. On dosing days, all assessments to be performed preinfusion, unless stated otherwise.
	1	2	3	8	15	22	
Relative day within a 28-day cycle:							
Immunogenicity	X					X	If at any time a patient experiences an IRR, attempt to obtain a blood sample for immunogenicity analysis as close to the onset of the event as possible, at the resolution of the event, and 30 d following the event. A portion of the sample taken for immunogenicity testing may be used for PK analysis.
Myoglobin (local)					X		Refer to Attachment 2 . If serum CK Grade ≥ 2 , test for serum and urine myoglobin.
CTCAE v4.0 grading	X			X	X	X	Throughout study as needed. Refer to Section 8.1.1 for reporting guidelines.
Concomitant medications	X			X	X	X	Throughout study as needed.
LY3022855 administration	Refer to Table JSCC.1 for dose frequency during Part A.						For LY3022855 and durvalumab: Part A doses: Refer to Table JSCC.1 .
Durvalumab administration	X				X		Part B doses and dose frequencies to be determined; refer to Section 7.2.2.2 for information.
Pharmacokinetics							
LY3022855 (predose on dosing days, unless noted otherwise)	X	X 2 h post-EOI C1D1 (± 1 h)	X 24 h post-EOI C1D1 (± 4 h)	X 48 h post-EOI C1D1 (± 4 h)	X	X	X The date and the time of all samples must be clearly and accurately recorded. EOI = end of infusion
Durvalumab (predose on dosing days, unless noted otherwise)	X	X Simultaneously with LY PK sample	X Simultaneously with LY PK sample	X Simultaneously with LY PK sample	X	X	X
Pharmacodynamics and tailoring							
Serum	X	X Simultaneously with LY PK sample	X Simultaneously with LY PK sample	X Simultaneously with LY PK sample	X	X	X Serum storage for correlative studies.
Plasma	X						Plasma storage for correlative studies.

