	1	2	3	8	15	22		
Relative day within a 28-day cycle:								
Myoglobin (local)	X				X		Refer to Attachment 2 . If serum CK Grade ≥ 2 , test for serum and urine myoglobin.	
CTCAE v4.0 grading	X			X	X	X	Throughout study as needed. Refer to Section 8.1.1 for reporting guidelines.	
Concomitant medications	X			X	X	X	Throughout study as needed.	
LY3022855 administration	Refer to Table JSCC.2 for dose frequency during Part A.						For LY3022855 and tremelimumab: Part A doses: Refer to Table JSCC.2 .	
Tremelimumab administration	X							
Pharmacokinetics								
LY3022855 (predose on dosing days, unless noted otherwise)	X	X 2 h post-EOI C1D1 (± 1 h)	X 24 h post-EOI C1D1 (± 4 h)	X 48 h post-EOI C1D1 (± 4 h)	X	X	X	The date and the time of all samples must be clearly and accurately recorded. EOI = end of infusion
Tremelimumab (predose on dosing days, unless noted otherwise)	X	X Simultaneously with LY PK sample	X Simultaneously with LY PK sample	X Simultaneously with LY PK sample	X	X	X	
Pharmacodynamics and tailoring								
Serum	X	X Simultaneously with LY PK sample	X Simultaneously with LY PK sample	X Simultaneously with LY PK sample	X	X	X	Serum storage for correlative studies.
Plasma	X							Plasma storage for correlative studies.
Whole blood	X	X			X			Gene expression analysis and other exploratory research.
Flow cytometry								
Immunophenotyping #1	X			X	X	X	CD14, CD16.	
Immunophenotyping #2	X			X	X	X	TBNK & T cell subset/activation panels	
Immunophenotyping #3	X						MDSC panel.	
Isoenzymes (central)							Refer to Attachment 2 . Obtain at additional time points, as clinically indicated.	
LVEF evaluation							Echocardiogram or MUGA scan. Obtain at additional time points, as clinically indicated.	

LY3022855 plus Tremelimumab Assessment (central or local laboratory indicated, if applicable)	Cycle 1 (Visit 1)						Comments Except for the Cycle 1, Day 1 visit, allowable windows are ± 3 days, unless otherwise indicated. On dosing days, all assessments to be performed preinfusion, unless stated otherwise.
	1	2	3	8	15	22	
Relative day within a 28-day cycle:	1	2	3	8	15	22	
Radiographic tumor assessment (CT/MRI)							Perform every 8 wk (± 7 d), starting on Cycle 2, Day 22.
Tumor measurement (palpable or visible)							
Tumor biopsy							For Part A (all cohorts) and Part B (ovarian cancer cohort only): An on-treatment tumor core needle or excisional biopsy to be performed 6-8 wk after starting study treatment.

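### The only post-dose partner-drug PK sample on Cycle 1 Day 1 is timed from the LY3022855 infusion, so a compliant draw can fall while durvalumab or tremelimumab is still running

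*Protocol*

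**What the plan says.** **Order and length of infusions.** Protocol Section 7.2.1: "For each combination regimen, LY3022855 will be administered first, followed by a 30-minute observation period"; durvalumab or tremelimumab comes next. This sets a minimum gap and no maximum. Sections 7.2.1.2 and 7.2.1.3 give each partner drug over 60 ±5 minutes. For a Grade 2 or lower infusion reaction, "the infusion rate of study drug may be decreased by 50% or interrupted until resolution of the event".

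**Cycle 1 sampling (Attachment 1, both combinations).** The LY3022855 row has a post-dose draw at "2 h post-EOI C1D1" (±1 h), then draws at 24 h (±4 h) and 48 h (±4 h). The partner rows have no clock of their own; each of these draws is marked "Simultaneously with LY PK sample". Other draws on dosing days are predose. The durvalumab row shows seven entries under six day columns. I read the first two as the Day 1 predose and 2 h samples.

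**Later sampling.** The Cycle 2 post-dose series follows Day 8. Durvalumab is given on Days 1 and 15 and tremelimumab on Day 1, so Day 8 is not a partner dosing day. Cycles 3 and 4 have predose draws only, followed by one at 30-day follow-up.

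**Use of the data.** Single-dose PK of each partner drug is a secondary objective (Protocol 5.2.2, SAP 4.2). Protocol 10.5 and SAP 6.9 use noncompartmental methods and name Cmax, with AUC, as a primary PK parameter for each drug.

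**The concern.** A noncompartmental Cmax is the highest concentration measured. For an intravenous drug it therefore needs a sample at or soon after the end of that drug's own infusion. Here the sample clock starts at the end of a different infusion, and the lower limit of the window comes before the partner drug has finished. A site can follow the schedule exactly and draw the partner sample mid-infusion, with nothing further until about 24 h.

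The error goes one way: a mid-infusion draw can lower the observed Cmax but not raise it. Because no later sample sits near a partner peak, the study has no second chance to measure it.

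**Working it through.** Let time 0 be the end of the LY3022855 infusion, g the gap before the partner starts, and D the partner infusion length. Partner end of infusion (EOI) = g + D. The sampling window is 2 ± 1 h, that is 1.0 to 3.0 h (width 2.0 h). The plan states no figure of its own to reproduce.

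**1. Dosing as written** (g = 0.5 h, D = 1.0 h)
- Partner infusion: 0.5 to 1.5 h.
- Part of the window during the infusion: 1.5 − 1.0 = 0.5 h; 0.5 / 2.0 = 25%. For D = 55 to 65 minutes, EOI is 1.42 to 1.58 h and the share is 21% to 29%.
- Share of dose given at 1.0 h: (1.0 − 0.5) / 1.0 = 50%, or 55% to 46% for 55 to 65 minutes.
- Nominal 2.0 h draw: 2.0 − 1.5 = 0.5 h, so 30 minutes after partner EOI.
- The other 75% of the window covers 0 to 90 minutes after partner EOI.

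**2. Late partner start** (D = 1.0 h)
- The exact 2 h draw is mid-infusion if g + 1.0 > 2.0, so g > 1.0 h. That is more than 30 minutes later than the earliest start.
- Share of dose given at 2 h: g = 1.25 h gives 75%; g = 1.5 h gives 50%.
- A compliant draw before any partner drug is given also needs g > 1.0 h. The pre-infusion share of the window is (1.25 − 1.0) / 2.0 = 12.5% at g = 1.25 h, and 25% at g = 1.5 h. For the exact 2 h draw to be pre-infusion, g must exceed 2.0 h.

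**3. Rate halved x minutes into a 60-minute infusion** (g = 30 minutes)
- Total length = x + 2(60 − x) = 120 − x minutes; partner EOI = 150 − x minutes.
- The exact 2 h (120-minute) draw is mid-infusion only if 150 − x > 120, so x < 30.
- Extreme case x = 0: EOI at 2.5 h; share given at 2 h = (2.0 − 0.5) / 2.0 = 75%; share of the window mid-infusion = (2.5 − 1.0) / 2.0 = 75%.

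**4. Effect on Cmax**
- Ignoring elimination and distribution during the infusion, observed / true Cmax is about max(f, r). Here f is the share of dose given at the draw and r is the 24 h concentration divided by the peak.
- The documents do not give r. Assuming r = 0.6 to 0.95, a draw at 1.0 h (f = 0.50) gives max(0.50, r) = 0.60 to 0.95, so Cmax is understated by 40% to 5%.
- Whenever f < r, the 24 h sample sets the value, so the loss in an affected profile cannot exceed 1 − r.

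**The case against.** The nominal design is sound. When dosing runs on time, the 2 h draw is already 30 minutes after the partner infusion, the same point a re-anchored sample would target. Section 8.4 treats collection times as targets, and nothing suggests that draws spread evenly over the window. This stands: 25% describes the window, not the proportion of samples.

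The Day 1 ECG row calls for a tracing 0 to 3 h after the partner infusion and wants ECGs taken before associated blood draws. If the 2 h draw is the associated one, it must follow partner EOI. The term is not defined, so this does not settle the matter. Reading EOI as the end of the last infusion would remove the problem, but the abbreviation sits in the LY3022855 row and the partner row defers to that sample.

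Actual times are recorded, up to five extra samples are allowed (8.2.2), the sponsor may change collection times (8.4), and SAP 6.3 asks for sufficient samples. These measures make a mid-infusion draw identifiable. None of them schedules a post-infusion one, and neither document defines a sufficient profile for Cmax.

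A reader might infer more than the documents support:
- That this is the only Day 1 partner sample. A predose sample is also scheduled, though it cannot inform Cmax.
- That pre-infusion draws follow from the written sequence. They need a partner start more than 60 minutes after LY3022855 ends, which is not forbidden but is not the plan.
- That any halved rate spoils the 2 h draw. Halving at or after minute 30 does not.
- That the result would be a false interaction signal in the geometric mean ratio with its 90% CI. Section 10.5 mentions that ratio and the comparison with historical monotherapy in separate sentences and does not say the ratio is against historical data.

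**Conclusion.** The defect is real in both combinations and limited in size. The sole post-dose same-day partner sample, which is also the only scheduled near-peak one, is tied to the wrong infusion. With dosing exactly as written, the first half hour of its two-hour window falls during the partner infusion, with as little as about 50% of the dose given. Delays or early rate reductions that the protocol allows extend the problem to the nominal time.

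The consequence is a possible downward error in partner single-dose Cmax. The documents do not allow it to be sized: they give neither the 24 h to peak ratio nor the distribution of actual draw times, and the 5% to 40% range rests on an assumed ratio. Any effect on AUC was not assessed. The analyses are descriptive and this is a secondary objective, so the point does not touch the primary safety aims. It is still worth correcting, because the affected quantity is a primary PK parameter and the remedy needs no extra draw.

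**What to change.** In Attachment 1, for both combinations:
- Time the first post-dose Cycle 1 Day 1 partner sample from the end of the durvalumab or tremelimumab infusion, for example 30 ± 15 minutes after it.
- Draw the LY3022855 tube at the same moment and record its actual time after the end of the LY3022855 infusion.
- Widen the LY3022855 window to match when the partner infusion runs late.

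In SAP 6.9, for Cycle 1 Day 1, leave out of the partner Cmax summary any profile with no sample between partner EOI and the 24 h sample, and report how many are left out.

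**Cost.** The number of draws and tubes is unchanged. With dosing as written, the new window is 1.5 + 0.25 to 1.5 + 0.75 = 1.75 to 2.25 h after LY3022855 ends, centred on the present nominal time. Patients are already kept for one hour after the first partner infusion, and Attachment 1 already times the post-infusion ECG and vital signs from that infusion. The downside is that the LY3022855 draw may fall later than 2 h, and beyond 3 h after a long delay. A partner start at 2 h, for instance, ends at 3 h and gives a draw at 3.5 h. This is why the LY3022855 row must be changed too.

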5.2.2. Secondary Objectives

The secondary objectives of this study are:

- To document the antitumor activity of each combination, LY3022855 with durvalumab, and LY3022855 with tremelimumab, in the treatment of patients with advanced solid tumors.
- To assess the development of antibodies against LY3022855, durvalumab, and tremelimumab (immunogenicity).
- To characterize the single-dose and multiple-dose pharmacokinetics (PK) of LY3022855 in combination with either durvalumab or tremelimumab, and the single-dose and multiple-dose PK of durvalumab and tremelimumab, each in combination with LY3022855.

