7.2.1.3. Tremelimumab

Patients are to receive tremelimumab I.V. on Day 1 of every cycle for the first 6 doses (Cycles 1-6). Starting with Cycle 7 (4 weeks after Dose 6 [Week 25]), tremelimumab will be dosed once every 3 cycles (12 weeks), that is, on Day 1 of Cycles 7, 10, 13, and so on, until disease progression.

Tremelimumab may be administered up to 3 days AFTER the scheduled dosing date. If, at any time, a dose is administered beyond the 3-day window, that dose is considered a dose delay. A delay of up to 28 days between administered doses is allowed for Cycles 1 through 6, and up to 60 days between doses for Cycles 7 and beyond.

Refer to [Attachment 9](#) for the tremelimumab dose volume calculation.

Tremelimumab will be administered at room temperature (approximately 25°C) by controlled infusion via an infusion pump into a peripheral or central vein. Following preparation of tremelimumab, the entire contents of the I.V. bag should be administered as an I.V. infusion over

approximately 60 minutes (± 5 minutes), using a 0.2- or 0.22- μm in-line filter. Less than 55 minutes is considered a deviation.

The I.V. line will be flushed with a volume of 0.9% (w/v) saline equal to the priming volume of the infusion set used after the contents of the I.V. bag are fully administered, or complete the infusion according to institutional policy to ensure the full dose is administered and document if the line was not flushed.

In the event that either preparation time or infusion time exceeds the time limits presented in this section, a new dose must be prepared from new vials. Tremelimumab does not contain preservatives, and any unused portion must be discarded.

A 1-hour observation period is required after the first infusion of tremelimumab. If no clinically significant infusion reactions are observed during or after the first cycle, subsequent infusion observation periods can be at the investigator's discretion (suggested 30 minutes after each tremelimumab infusion).

Patients will be monitored during and after the infusion with assessment of vital signs at the times specified in this study protocol.

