7.2.2. Part A: Dose Escalation (Phase 1a)

By nature of being a dose-escalation study, data will be evaluated on an ongoing basis until the MTD is determined. Safety data, in particular AEs, will be the primary criteria for the dose escalation. No dose escalation can occur without prior discussion and agreement between the investigator, the Lilly study team, and the collaborator; the decision will be documented in writing.

Based on the ongoing safety reviews, modifications to the dose-escalation strategy or other design elements may be made via protocol amendment to ensure patient safety. No intrapatient dose escalation is permitted for any patient. Dose escalation may be ceased at any time based on available safety and PK behavior.

In Part A, study drugs for the LY3022855-plus-durvalumab and LY3022855-plus-tremelimumab combinations may be administered at the dose regimens shown in [Table JSCC.1](#) and

Table JSCC.2, respectively. Refer to Section 7.2.2.2 for further details on the planned dose-escalation method, proceeding from Cohorts D1a and T1a.

Table JSCC.1. Part A (Dose Escalation) Dose Regimens for the LY3022855-plus-Durvalumab Combination, by Cohort

Cohort	LY3022855		Durvalumab	
	Dose (mg)	Frequency	Dose (mg)	Frequency
D1a	25	QW	750	Q2W
	D1b ^a	25 Days 1, 8, and 15 of each cycle	750	Q2W
	D1c	25 Q2W	750	Q2W
D2a	50	QW	750	Q2W
	D2b ^a	50 Days 1, 8, and 15 of each cycle	750	Q2W
	D2c	50 Q2W	750	Q2W
D3a	75	QW	750	Q2W
	D3b ^a	75 Days 1, 8, and 15 of each cycle	750	Q2W
	D3c	75 Q2W	750	Q2W
D4a	100	QW	750	Q2W
	D4b ^a	100 Days 1, 8, and 15 of each cycle	750	Q2W
	D4c	100 Q2W	750	Q2W

Abbreviations: QW = weekly; Q2W = every 2 weeks.

Note: A cycle is defined as 28 days (4 weeks). QW refers to dosing on Days 1, 8, 15, and 22 of each cycle; Q2W refers to dosing on Days 1 and 15 of each cycle.

^a Enrollment to the Dnb cohort will occur only if ≥ 2 DLTs are observed after Cycle 1, Day 21 of the corresponding Dna cohort.

Table JSCC.2. Part A (Dose Escalation) Dose Regimens for the LY3022855-plus-Tremelimumab Combination, by Cohort

Cohort	LY3022855		Tremelimumab	
	Dose (mg)	Frequency	Dose (mg)	Frequency ^a
T1a	50	QW	75	Q4W
	T1b ^b	50 Days 1, 8, and 15 of each cycle	75	Q4W
	T1c	50 Q2W	75	Q4W
T2a	100	QW	75	Q4W
	T2b ^b	100 Days 1, 8, and 15 of each cycle	75	Q4W
	T2c	75 Q2W	75	Q4W
T3a	100	QW	225	Q4W
	T3b ^b	100 Days 1, 8, and 15 of each cycle	225	Q4W
	T3c	100 Q2W	225	Q4W
	T3d	75 QW	225	Q4W
T4a	100	QW	750	Q4W
	T4b	100 Q2W	750	Q4W

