10.5. Pharmacokinetic Analyses

Pharmacokinetic analyses will be conducted on patients who have received at least one dose of the study drug and have had samples collected. Pharmacokinetic parameter estimates for LY3022855, durvalumab, and tremelimumab will be calculated by standard noncompartmental methods of analysis. The primary parameters for analysis will be maximum concentration (C_{max}) and area under the plasma concentration-time curve (AUC; AUC from time zero to last measurable plasma concentration [$AUC_{0-tlast}$] and AUC from time zero to infinity [$AUC_{0-\infty}$]) of each of the study drugs. Other noncompartmental parameters, such as time of half-life ($t_{1/2}$), apparent clearance (CL/F), and apparent volume of distribution (V/F) for each study drug may be reported. Additional exploratory analyses will be performed if warranted by data and other validated PK software programs (for example, NONMEM) may be used if appropriate and approved by Global Pharmacokinetic management. The version of any software used for the analysis will be documented and the program will meet the Lilly requirements of software validation.

Pharmacokinetic parameter estimates will be evaluated to delineate the effects of dose proportionality, target-mediated drug disposition, and drug accumulation. Log-transformed C_{max} and AUC estimates will be assessed to estimate ratios of geometric means and the corresponding 90% CIs. The potential effect of durvalumab-mediated PD-L1 inhibition and/or tremelimumab-mediated CTLA-4 inhibition on the exposure of LY3022855, and the effect of LY3022855-mediated CSF-1R inhibition on the exposure of tremelimumab and/or durvalumab will be assessed using historical monotherapy exposure data for each of the 3 study drugs.

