Thyroid function (central)	X						Refer to Attachment 2 . Free T3 and free T4 will be measured only if TSH is abnormal or if there is clinical suspicion of an AE related to the endocrine system.
Pancreas function (central)	X						Refer to Attachment 2 .
Tumor markers (local)	X						If clinically indicated.
Pharmacogenetic sample							Refer to the laboratory manual. Collect once. Sample can be collected at any time, if not collected on C1D1.
Immunogenicity		X					If at any time a patient experiences an IRR, attempts to obtain a blood sample for immunogenicity analysis as close to the onset of the event as possible, at the resolution of the event, and 30 days following the event. A portion of the sample taken for immunogenicity testing may be used for PK analysis.
Myoglobin (local)	X	X			X	X	Refer to Attachment 2 . If serum CK Grade ≥ 2 , test for serum and urine myoglobin.
CTCAE v4.0 grading	X	X			X	X	Throughout study as needed. Refer to Section 8.1.1 for reporting guidelines.
Concomitant medications	X	X			X	X	Throughout study as needed.
LY3022855 administration	Refer to Table JSCC.1 for dose frequency during Part A.						For LY3022855 and durvalumab: Part A doses: Refer to Table JSCC.1 . Part B doses and dose frequencies to be determined; refer to Section 7.2.2.2 for information.
Durvalumab administration	X				X		
Pharmacokinetics							
LY3022855 (predose on dosing days, unless noted otherwise)	X	X	X 2 h post-EOI C2D8 (± 1 h)	X 24 h post-EOI C2D8 (± 4 h)	X 48 h post-EOI C2D8 (± 4 h)	X	The date and the time of all samples must be clearly and accurately recorded. EOI = end of infusion
Durvalumab (predose on dosing days, unless noted otherwise)	X	X	X Simultaneously with LY PK sample	X Simultaneously with LY PK sample	X Simultaneously with LY PK sample	X	
Pharmacodynamics and tailoring							
Serum	X	X	X Simultaneously with LY PK sample	X Simultaneously with LY PK sample	X Simultaneously with LY PK sample	X	Serum storage for correlative studies.
Plasma			X				Plasma storage for correlative studies.
Whole blood	X				X		Gene expression analysis and other exploratory research.
Flow cytometry							
Immunophenotyping #1	X	X			X		CD14, CD16.
Immunophenotyping #2	X	X			X		TBNK & T cell subset/activation panels.
Immunophenotyping #3	X						MDSC panel.

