Coagulation (local)	X						Refer to Attachment 2 . Obtain prior to tumor biopsy. Additional assessments as clinically indicated.
Thyroid function (central)	X						Refer to Attachment 2 . Free T3 and free T4 will be measured only if TSH is abnormal or if there is clinical suspicion of an AE related to the endocrine system.
Pancreas function (central)	X						Refer to Attachment 2 .
Tumor markers (local)	X						If applicable.
Pharmacogenetic sample							Refer to the laboratory manual. Collect once. Sample can be collected at any time, if not collected on C1D1.
Immunogenicity		X					If at any time a patient experiences an IRR, attempts to obtain a blood sample for immunogenicity analysis as close to the onset of the event as possible, at the resolution of the event, and 30 days following the event. A portion of the sample taken for immunogenicity testing may be used for PK analysis.
Myoglobin (local)	X	X			X	X	Refer to Attachment 2 . If serum CK Grade ≥ 2 , test for serum and urine myoglobin.
CTCAE v4.0 grading	X	X			X	X	Throughout study as needed. Refer to Section 8.1.1 for reporting guidelines.
Concomitant medications	X	X			X	X	Throughout study as needed.
LY3022855 administration	Refer to Table JSCC.2 for dose frequency during Part A.						For LY3022855 and tremelimumab: Part A doses: Refer to Table JSCC.2 .
Tremelimumab administration	X						
Pharmacokinetics							
LY3022855 (predose on dosing days, unless noted otherwise)	X	X	X 2 h post-EOI C2D8 (± 1 h)	X 24 h post-EOI C2D8 (± 4 h)	X 48 h post-EOI C2D8 (± 4 h)	X	The date and the time of all samples must be clearly and accurately recorded. EOI = end of infusion
Tremelimumab (predose on dosing days, unless noted otherwise)	X	X	X Simultaneously with LY PK sample	X Simultaneously with LY PK sample	X Simultaneously with LY PK sample	X	

LY3022855 plus Tremelimumab Assessment (central or local laboratory indicated, if applicable)	Cycle 2 (Visit 2)						Comments
							Except for the Cycle 1, Day 1 visit, allowable windows are ± 3 days, unless otherwise indicated. On dosing days, all assessments to be performed preinfusion, unless stated otherwise.
Relative day within a 28-day cycle:	1	8	9	10	15	22	
Pharmacodynamics and tailoring							
Serum	X	X	X Simultaneously with LY PK sample	X Simultaneously with LY PK sample	X Simultaneously with LY PK sample	X	Serum storage for correlative studies.
Plasma		X					Plasma storage for correlative studies.

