6.9. Pharmacokinetic Analyses

Pharmacokinetic analyses will be conducted on patients who have received at least 1 dose of the study drug and have had samples collected. Pharmacokinetic parameter estimates for LY3022855, durvalumab, and tremelimumab will be calculated by standard noncompartmental methods of analysis. The primary parameters for analysis will be maximum concentration (C_{max}) and area under the concentration-time curve ($AUC_{0-tlast}$, $AUC_{0-\infty}$) of each of the study drugs. Other noncompartmental parameters, such as time of half-life ($t_{1/2}$), apparent clearance (CL/F), and apparent volume of distribution (V/F) for each study drug may be reported. Additional exploratory analyses will be performed if warranted by data and other validated PK software programs (for example, NONMEM) may be used if appropriate and approved by Global Pharmacokinetic management. The version of any software used for the analysis will be documented and the program will meet the Lilly requirements of software validation.

Pharmacokinetic parameter estimates will be evaluated to delineate the effects of dose proportionality, target-mediated drug disposition, and drug accumulation. Log-transformed C_{max}

and AUC estimates will be assessed to estimate ratios of geometric means and the corresponding 90% CIs. The potential effect of durvalumab-mediated programmed death-ligand 1 (PD-L1) inhibition and/or tremelimumab-mediated cytotoxic T-lymphocyte-associated protein 4 (CTLA-4) inhibition on the exposure of LY3022855 and the effect of LY3022855-mediated CSR-1 inhibition on the exposure of tremelimumab and/or durvalumab will be assessed using historical monotherapy exposure data for each of the 3 study drugs.

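### After the first dose, the only infusion-timed PK samples follow Cycle 2 Day 8, so repeat-dose Cmax is not observed for durvalumab, tremelimumab or Q2W LY3022855

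*Protocol*

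**What the plan says.** Protocol 5.2.2 makes it a secondary objective to characterize single-dose and multiple-dose PK of LY3022855 and "the single-dose and multiple-dose PK of durvalumab and tremelimumab, each in combination with LY3022855". Protocol 10.5 and SAP 6.9 specify standard noncompartmental methods. In the SAP's words, "The primary parameters for analysis will be maximum concentration", together with AUC, for each study drug. Both sections also plan to evaluate drug accumulation and to estimate geometric mean ratios of Cmax and AUC. Protocol 10.5 adds that the "effect of LY3022855-mediated CSF-1R inhibition on the exposure of tremelimumab and/or durvalumab will be assessed using historical monotherapy exposure data".

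Attachment 1 sets the sampling. In both combinations, samples at 2, 24 and 48 h after an end of infusion are scheduled twice: after Cycle 1 Day 1, and after Cycle 2 Day 8 ("2 h post-EOI C2D8" is the first of the second set). The durvalumab and tremelimumab rows carry the instruction "Simultaneously with LY PK sample". The Cycle 3 and Cycle 4 samples are Day 1 predose only. After those, only the 30-day follow-up sample is scheduled.

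The dosing days are:
- Durvalumab (7.2.1.2): "Patients are to receive durvalumab I.V. on Days 1 and 15 of every cycle".
- Tremelimumab (7.2.1.3): "Patients are to receive tremelimumab I.V. on Day 1 of every cycle for the first 6 doses".
- Every-2-week LY3022855 (note to Table JSCC.1): "Q2W refers to dosing on Days 1 and 15 of each cycle".

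**The concern.** The second post-infusion block suits LY3022855 given weekly or on Days 1, 8 and 15, because Cycle 2 Day 8 is a dosing day in those schedules. It does not suit the partner drug, which every patient receives, or LY3022855 given every 2 weeks.

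A noncompartmental Cmax is an observed value. Without a sample near the end of a later infusion there is no repeat-dose Cmax, and neither document says what is reported in its place. If the largest Cycle 2 concentration were used, it would be a level from about a week after dosing. Set against a true historical peak, it would look like reduced exposure with no interaction present. In the every-2-week cohorts a site would also be asked to time samples from an infusion that does not take place. Table JSCC.3 allows such a cohort to be the MTD, and Attachment 1 leaves the Part B frequency open, so the gap could carry into Part B.

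**Working it through.** **1. Time since last infusion in the Cycle 2 block.** Number study days from Cycle 1 Day 1 = day 1. Cycle 2 Day 1 is day 29 and Cycle 2 Day 8 is day 36.

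| Drug and schedule | Last infusion before or on day 36 | Dose number | Hours at the three samples |
|---|---|---|---|
| LY3022855 weekly | day 36 | 6 | 2, 24, 48 |
| LY3022855 Days 1/8/15 | day 36 | 5 | 2, 24, 48 |
| LY3022855 every 2 weeks | day 29 | 3 | 170, 192, 216 |
| Durvalumab every 2 weeks | day 29 | 3 | 170, 192, 216 |
| Tremelimumab every 4 weeks | day 29 | 2 | 170, 192, 216 |

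For the last three rows, (36 − 29) × 24 = 168 h, plus 2, 24 and 48 h. Across all scheduled on-treatment samples after the first dose, the shortest interval since one of their infusions is 168 h. The table extraction leaves it unclear whether the last Cycle 2 sample is Day 15 or Day 22; the result is the same either way. The dosing windows do not put a Day 1 or Day 15 dose on Day 8.

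**2. Size of the shortfall if the highest Cycle 2 value were called Cmax.** No half-life is stated. The only indication is Protocol 6.1.3, which equates 4 to 5 half-lives with 6 months: 180/5 = 36 days and 180/4 = 45 days. That may reflect only the longest-lived drug, so 21 and 7 days are added as assumptions. With one compartment, level at 7 days ÷ peak of the same dose = 2^(−7/half-life):

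| Half-life (days) | 45 | 36 | 21 (assumed) | 7 (assumed) |
|---|---|---|---|---|
| Fraction of peak | 0.90 | 0.87 | 0.79 | 0.50 |

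**3. Repeat-dose AUC.** Same model, unit doses, linear-up/log-down rule, starting from the Cycle 2 Day 1 predose value. Example: every-2-week drug, half-life 21 days, doses at days 0, 14 and 28, with day 42 assumed sampled.
- k = ln 2/21 = 0.0330 per day.
- Predose at day 28: 0.397 + 0.630 = 1.027. Peak: 2.027.
- Day 35: 2.027 × 0.794 = 1.609. Day 42: 2.027 × 0.630 = 1.277.
- True AUC = (2.027 − 1.277)/0.0330 = 22.7.
- Estimated AUC = 7 × (1.027 + 1.609)/2 + (1.609 − 1.277)/0.0330 = 9.2 + 10.1 = 19.3, which is 85% of true.

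At half-lives of 7, 21 and 45 days the results are 67%, 85% and 89% for an every-2-week drug, and 67%, 86% and 91% for tremelimumab. The rule matters: plain linear trapezoids give 78%, 88% and 91% for tremelimumab. Log-linear back-extrapolation to the dose time returns 100% in every case.

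**4. First-dose partner peak.** If the end of infusion is that of LY3022855, the partner infusion ends 30 min (observation, 7.2.1) + 60 min (7.2.1.2, 7.2.1.3) = 1.5 h later. The 2 h ± 1 h draw then falls between 1 − 1.5 = −0.5 h and 3 − 1.5 = +1.5 h from the end of the partner infusion, so it may be taken mid-infusion.

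**5. Patients.** Protocol 10.1 gives up to 36 + 40 on durvalumab and up to 42 on tremelimumab: 118. The every-2-week LY3022855 cohorts open only after DLTs, at most one per combination at 3 to 6 patients. With 40 in Part B if such a schedule is chosen, that is 0 to 6 + 6 + 40 = 52.

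**The case against.** The objective is to characterize multiple-dose PK. Neither document says that Cmax must be reported for repeat doses, and the AUCs named are to the last measurable sample and to infinity, not over a dosing interval. First-dose profiles plus accumulation would fit that wording. Accumulation is recoverable from troughs or from matched Day 8 levels in Cycles 1 and 2. This stands and limits the damage. It does not explain how multiple-dose PK is to be described by the named primary parameters.

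A reader might infer that the plan directs a biased Cmax ratio against historical monotherapy. The documents do not support that. In Protocol 10.5 the geometric mean ratio sentence and the historical comparison are separate, the latter speaks only of exposure, and nothing tells the analyst to report a 7-day level as Cmax. Actual sampling times are recorded. A reader might also take 0.50 as the expected ratio, but it rests on an assumed 7-day half-life.

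Remedies exist: up to 5 added samples (8.2.2), sponsor changes to collection times (8.4), and population modelling (10.5). All are discretionary, and a model would give a predicted peak, not an observed one.

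**Conclusion.** The point holds as a gap between the stated objective and the sampling schedule. With the nominal schedule followed exactly, repeat-dose Cmax is unobserved for durvalumab and tremelimumab in every cohort and for LY3022855 in every-2-week cohorts, where the Day 8 label also has no infusion behind it. This follows from the dosing and sampling days alone. The size of any understatement is conditional: it needs the highest Cycle 2 value to be used as Cmax, a one-compartment decline, and an assumed half-life.

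AUC is a secondary point, since its bias disappears with back-extrapolation. It would be wrong to conclude that multiple-dose PK cannot be described at all. Single-dose LY3022855 PK, repeat-dose LY3022855 PK in weekly and Days 1/8/15 cohorts, and accumulation are unaffected. It would equally be wrong to call the first-dose partner peak secure, given the timing in step 4 of the working.

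The figure of about 118 is a ceiling: it assumes maximum Part A enrolment and that every patient reaches Cycle 2. The objective is descriptive and secondary, with no decision rule attached. It should still be fixed, because the correction is small.

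**What to change.** Change sampling only; no dosing change is implied.

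- **Durvalumab arms:** anchor the 2, 24 and 48 h Cycle 2 block, with its linked serum draws, to Days 15, 16 and 17, when both drugs are given in every schedule. Keep the existing Day 8 draw for the matched comparison. Time the durvalumab post-infusion sample to the end of its own infusion.
- **Tremelimumab arms:** keep the Day 8 block for LY3022855 in weekly and Days 1/8/15 cohorts. Add one tremelimumab post-infusion draw at the existing Cycle 2 Day 1 visit, timed to its own end of infusion.
- **Every-2-week LY3022855 cohorts:** anchor the block to an LY3022855 dosing day, Cycle 2 Day 1 or Day 15.

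Otherwise, limit the multiple-dose Cmax and AUC claim to LY3022855 in weekly and Days 1/8/15 cohorts, and report troughs and matched Day 8 accumulation for the rest. If repeat-dose AUC is kept, the SAP should state how the missing peak is handled.

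The cost is a change to the schedule table and possibly one extra draw. In durvalumab arms the number of visit days is unchanged, as Days 9 and 10 become Days 16 and 17. The real downside is comparability: weekly LY3022855 would be profiled after dose 7 rather than dose 6, and Days 1/8/15 after dose 6 rather than dose 5. Those profiles would not match any already collected at Cycle 2 Day 8, nor those in the tremelimumab arms.
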